D/C	Discontinue
EC	Ethics Committee, synonymous to Institutional Review Board and Independent Ethics Committee
ECG	Electrocardiogram
ECOG	Eastern Cooperative Oncology Group
eCRF	Electronic case report form
EDoR	Expected duration of response
e.g.	Exempli gratia (for example)
EGFR	Epidermal growth factor receptor
ER	Estrogen receptor
FACS	Fluorescence Activated Cell Sorting
FAS	Full analysis set
FDA	Food and Drug Administration
FDG-PET	Fluorodeoxyglucose (FDG)-positron emission tomography (PET)
GCP	Good Clinical Practice
GFR	Glomerular Filtration Rate
GGT	Gamma Glutamyl Transferase
GI	Gastrointestinal
GLP	Good Laboratory Practice
GMP	Good Manufacturing Practice
HBsAg	Hepatitis B surface antigen
HBV	Hepatitis B virus
hCG	Human chorionic gonadotropin

Abbreviation or	Definition/Explanation
HCO_3^-	Bicarbonate
HCV	Hepatitis C virus
HER-2	Human epidermal receptor-2
HIV	Human immunodeficiency virus
HR	Heart rate
hr	Hour or hours
IB	Investigator's Brochure
IC_{50}	Half maximal inhibitory concentration
ICF	Informed consent form
ICH	International Conference on Harmonization
IDMC	Independent Data Monitoring Committee
i.e.	Id est (that is)
IEC	Independent ethics committee
$\text{IFN}\gamma$	Interferon-gamma
IgE	Immunoglobulin E
IgG	Immunoglobulin G
IHC	Immunohistochemistry
IL	Interleukin
ILS	Interstitial lung disease
IM	Intramuscular
IMT	Immunomodulatory therapy
INR	International normalized ratio
IP	Investigational product
irAE	Immune-related adverse event
IRB	Institutional review board
irRECIST	Immune-related Response Evaluation Criteria in Solid Tumors
ITT	Intent-to-Treat
IU	International unit
IV	Intravenous, intravenously
LDH	Lactate dehydrogenase
LLQ	Lower limit of quantitation
mAb	Monoclonal antibody
mPEPI	Modified preoperative endocrine prognostic index
M	Metastasis (in pathologic tumor-node-metastasis system)
MDSC	Myeloid-derived suppressor cell
MedDRA	Medical Dictionary for Regulatory Activities
MHLW	Minister of Health, Labor, and Welfare
miRNA	Micro-ribonucleic acid

Abbreviation or	Definition/Explanation
MRI	Magnetic resonance imaging
MRSD	Maximum recommended starting dose
MTD	Maximum tolerated dose
N	Node (in pathologic tumor-node-metastasis system)
NCI	National Cancer Institute
NOAEL	No-observed-adverse-effect level
NOEL	No-observed-effect-level
OAE	Other significant adverse event
ORR	Objective response rate
OS	Overall survival
PBMC	Peripheral blood mononuclear cell
PD	Progressive disease
PD-1	Programmed cell death 1
PD-L1	Programmed cell death ligand 1

Title	A phase II trial with safety run-in of neoadjuvant therapy with an aromatase inhibitor in combination with durvalumab (MEDI4736) in postmenopausal patients with hormone-receptor-positive breast cancer.
Short Title	Neoadjuvant study in breast cancer with durvalumab and aromatase inhibitor
Protocol Number	MCC 19803
IND	Exempt
Clinical Phase	Phase II
Design	This is a multi-center, open label, phase II study which will assess the efficacy and safety of an aromatase inhibitor (anastrozole) in combination with durvalumab in patients with hormone-receptor-positive breast cancer.
Study Duration	Enrollment period: 28 months Follow up: Up to 5 years.
Study Center(s)	1. Moffitt Cancer Center; 2. TBD
Objectives	Primary: To determine the efficacy of an aromatase inhibitor with durvalumab in achieving the modified Preoperative Endocrine Prognostic Index (mPEPI) Score of 0. Secondary: 1. Safety and tolerability 2. Objective clinical response rate (cRR: clinical CR and PR) at up to 24 weeks. 3. Pathologic complete response rate (pCR) at up to 24 weeks (defined as complete absence of invasive cancer in breast and axillary lymph nodes). 4. To determine recurrence free survival. Exploratory: 1. To assess immune cell changes (phenotype and functionality) in tumor before, during, and after treatment. 2. To assess cytokine patterns before, during, and after treatment. 3. To assess biomarkers that may correlate with clinical outcome.
Number of Subjects	Up to 46 expected to enroll. Up to 46 expected to be treated. 42 expected to complete treatment (including 6 from safety run-in phase).
Main Eligibility	Inclusion Criteria:

Criteria	
 • Female 18 years of age or older. • ECOG performance status 0 or 1. • Postmenopausal. • Invasive breast cancer; clinical T2-T4c, any N, M0, with goal of definitive surgery after completion of neoadjuvant therapy. • Palpable tumor which size can be measured bidimensionally by tape, ruler or caliper technique, with a largest diameter > 2.0 cm. • Invasive breast cancer is estrogen receptor positive at > 66% or with an Allred score of 6, 7 or 8. • Invasive breast cancer is Human Epidermal Growth Factor Receptor 2 (HER2) negative. • Patients must agree to provide tissue at baseline and at definitive surgery (from the procedure) and undergo a biopsy at baseline and after one cycle of treatment. • Adequate laboratory parameters. 
Exclusion Criteria:
 
 • Inflammatory breast cancer. • Excisional biopsy of breast cancer. • Hormone replacement therapy of any type within one week prior to registration. • Surgical axillary staging procedure prior to study entry. • Any treatment for this cancer prior to study entry • History of ipsilateral invasive breast cancer regardless of treatment or ipsilateral ductal carcinoma in situ treated with radiotherapy or endocrine therapy or contralateral invasive breast cancer at any time. • History of another primary malignancy except for malignancy treated with curative intent and with no known active disease ≥ 5 years or adequately treated non-melanoma skin cancer or lentigo maligna without evidence of disease or adequately treated carcinoma in situ without evidence of disease e.g., cervical cancer in situ. • Prior use of PD-1, PD-L1 or CTLA-4 inhibitors • Active or prior documented autoimmune or inflammatory disorders within the past 5 years. • Current or prior use of immunosuppressive medication within 14 days before the first dose of study drug. • Clinically significant cardiovascular disease. • Currently active systemic infection. • History of HIV infection or chronic hepatitis B or C. • History of previous clinical diagnosis of tuberculosis, uncontrolled seizures, organ transplant, primary immunodeficiency, interstitial lung disease (ILD)/pneumonitis. • Receipt of live attenuated vaccination within 30 days of first
----------	--

	
dose of study drug.
 
 • Weighing 30 kg or less.
Study Product, Dose, Route, Regimen	
Durvalumab, 1500 mg (equivalent to 20 mg/kg) IV Q4W, on Day 1 of each 28-day cycle x 6 cycles (6 months)
 
Anastrozole 1 mg PO QD [in the post DLT period, as per standard of care, it is OK to switch to another AI (letrozole 2.5 mg or exemestane 25 mg PO daily) for intolerance such as hot flash or joint ache that is attributed to AI].

Duration of administration	Six months prior to definitive surgery
Statistical Methodology	
Safety Analysis: will include all subjects who received at least 1 dose of AI or durvalumab.
 
Efficacy Analysis: will include all subjects who received at least one dose of AI and one dose of durvalumab.

1 STUDY OBJECTIVES AND ENDPOINTS

1.1 Study Objectives

1.1.1 Primary Objective

- To evaluate the efficacy of an aromatase inhibitor with durvalumab

1.1.2 Secondary Objectives

- To evaluate safety and tolerability of the combination of an aromatase inhibitor and durvalumab
- To evaluate objective clinical response rate
- To evaluate pathologic complete response rate (pCR)
- To evaluate recurrence free survival.

1.1.3 Exploratory Objective and Endpoints

- To assess immune cell changes (phenotype and/or functionality) in tumor before, during and after treatment.
- To assess cytokine patterns before, during and after treatment.
- To evaluate biomarkers that may correlate with clinical outcome.

1.2 Study Endpoints

1.2.1 Primary Endpoints

- Rate of modified Preoperative Endocrine Prognostic Index (mPEPI) Score of 0.

1.2.2 Secondary Endpoints

- Type, incidence, severity, attribution and timing of adverse events.
- Objective clinical response rate (cRR = clinical CR + PR) at up to 24 weeks.
- Pathologic complete response rate (pCR) at time of definitive surgery (defined as complete absence of invasive cancer in breast and axillary lymph nodes).
- Recurrence free survival defined as the time between first treatment and disease recurrence.

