4.6 Withdrawal of Subjects from Study Treatment and/or Study

4.6.1 Permanent discontinuation of investigational product

An individual patient will not receive any further investigational product if any of the following occur in the patient in question:

1. An individual patient will not receive any further durvalumab if their weight falls to 30kg or less
2. Withdrawal of consent or lost to follow-up
3. Adverse event that, in the opinion of the investigator or the sponsor, contraindicates further dosing
4. Patient is determined to have met one or more of the exclusion criteria for study participation at study entry and continuing investigational therapy might constitute a safety risk
5. Any AE that meets criteria for discontinuation as defined in Section 10.3 and Appendix 1.
6. Dose-limiting toxicity (as defined in section 4.2)
7. Grade ≥ 3 infusion reaction
8. Patient noncompliance that, in the opinion of the investigator or sponsor, warrants withdrawal; e.g., refusal to adhere to scheduled visits
9. Initiation of alternative anticancer therapy including another investigational agent
10. Confirmation of PD and investigator determination that the patient is no longer benefiting from treatment with durvalumab
11. Subjects who are permanently discontinued from receiving investigational product will be followed for safety per Section 15.4 and Appendix 1, including the collection of any protocol-

specified blood specimens, unless consent is withdrawn or the subject is lost to follow-up or enrolled in another clinical study. All subjects will be followed for recurrence free survival. Subjects who decline to return to the site for evaluations will be offered follow-up by phone every 3 months as an alternative.

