5.1 Inclusion Criteria

Yes/No (Response of "no" = patient ineligible)

- _____ 5.1.1 Able to provide a written informed consent and any locally-required authorization (e.g., HIPAA in the USA) prior to performing any protocol-related procedures, including screening evaluations.
- _____ 5.1.2 Female age \geq 18 years at time of study.
- _____ 5.1.3 Eastern Cooperative Oncology Group (ECOG) performance status of 0 or 1.
- _____ 5.1.4 Postmenopausal, defined as meeting at least 1 of the following criteria:
 - Age \geq 60
 - Prior bilateral oophorectomy
 - Age $<$ 60 with a uterus AND amenorrhea for at least the past 12 months (in the absence of chemotherapy, tamoxifen, toremifene, or ovarian suppression)
 - Age $<$ 60 without a uterus AND follicular stimulating hormone (FSH) and estradiol in the postmenopausal range per local normal range
- _____ 5.1.5 Clinical T2-T4c, any N, M0 by AJCC 8th edition, with the goal being definitive surgery after completion of neoadjuvant therapy.
 - The tumor is palpable and its size can be measured bidimensionally by tape, ruler or caliper technique
 - The largest tumor diameter is $>$ 2.0 cm
- _____ 5.1.6 Pathologic confirmation of invasive breast cancer that is estrogen receptor (ER) positive with an Allred score of 6, 7 or 8. If an Allred Score is not reported on the diagnostic pathology report, ER positivity in $>$ 66% cells is eligible. If ER positivity is \leq 66%, the staining intensity (weak, intermediate, strong) is needed to calculate the Allred Score to determine eligibility.
- _____ 5.1.7 Invasive breast cancer is Human Epidermal Growth Factor Receptor 2 (HER2) negative defined as 0 or 1+ by immunohistochemistry (IHC) or with an in situ hybridization (ISH) ratio (HER2 gene copy/chromosome 17) $<$ 2.
- _____ 5.1.8 Documentation of mammogram and ultrasound [including ductal carcinoma in situ (DCIS) and invasive cancer] of the diseased breast performed within 60 days prior to enrollment. Mammogram for the unaffected contralateral breast is required within 12 months prior to enrollment.

_____ 5.1.9 Adequate organ and marrow function as defined below, laboratory values obtained \leq 14 days prior to enrollment:

- Hemoglobin \geq 9.0 g/dL
- Absolute neutrophil count (ANC) $\geq 1.5 \times 10^9/L$ (≥ 1500 per mm 3)
- Platelet count $\geq 100 \times 10^9/L$ ($\geq 100,000$ per mm 3)

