6.1.2 Durvalumab

Durvalumab will be administered as follows:

Durvalumab, 1500 mg via IV infusion Q4W (equivalent to 20 mg/kg Q4W) on Day 1 of each 28-day cycle for 6 cycles (6 doses – 6 months).

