6.8 Duration of Therapy

Individual study patients may remain on treatment with an AI in combination with durvalumab until they experience intolerable toxicity, confirmed disease progression, or the investigator determines that the subject is no longer benefiting from treatment (more details are provided in section 4.6.1).

Patients will receive a maximum treatment with 6 cycles of durvalumab.

After the first 6 months, patients will continue receiving the AI at the discretion of the treating physician as per standard of care.

Patients who discontinue active treatment will be followed for recurrence free survival for up to 5 years or until the sponsor ends the study.

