¹² Mammogram, ultrasound of the ipsilateral breast within 60 days of the start of treatment. MRI of ipsilateral breast at baseline, end of cycle 1 (+/- 7 days), and at end of treatment prior to definitive surgery. Mammogram of the contralateral breast within 12 months of the start of treatment. Staging scans (CT chest, abdomen +/- pelvis and bone scan or PET/CT) should be considered, per institutional standard practice. Otherwise, staging scans should be obtained if clinically indicated.

¹³ If tumor assessment by exam is performed at screening within 7 days prior to C1D1 of treatment, no need to repeat tumor assessment by exam on C1D1.

¹⁴ MRI of ipsilateral breast at end of cycle 1 may be omitted at the discretion of the PI.

¹⁵ mPEPI score will include tumor size and nodal status based on final pathology report for the definitive surgery as well as Ki67 value of the tumor from the definitive surgery.

¹⁶ EOT is defined as the end of cycle 6 (28 +/- 7 days from C6D1) . For subjects who discontinue treatment early, EOT is considered as visit where the decision is made to discontinue treatment. All required procedures may be completed within ± 7 days of the EOT visit. Repeat imaging disease assessment is not required if performed within 28 days prior to the end of treatment visit.

¹⁷ First follow up visit will occur 90 to 97 days from last study treatment (durvalumab). The time to first follow up visit may be longer than 97 days, but in no case should it be <90 days. If first study visit is completed before 90 days after last durvalumab, the patient will be contacted 90 to 97 days following the last treatment to assess for adverse events. After all study therapy has been completed, patients will be followed for recurrence and survival for up to 5 years after registration (every 6 months +/- 1 month per either medical records or phone calls).

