11.2.2 Efficacy Analyses

Primary Endpoint: A Simon's two-stage Optimum design will be used in which the drug will be determined to be efficacious if 7 or more patients achieve an mPEPI of 0. The study will stop after the first 14 patients are enrolled if 1 or fewer patients achieve an mPEPI of 0.

Secondary Endpoints: The best response, including complete response (CR), partial response (PR), stable disease (SD), or progressive disease (PD), for each patient will also be summarized with 95% confidence intervals. Descriptive statistics will be used to

summarize all patient characteristics, treatment administration and compliance. Kaplan-Meier curves will be used to estimate the median recurrence free survival time.

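### Recurrence free survival starts at first treatment but counts only recurrence, so progression before surgery is not an event

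*Combined protocol and SAP*

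**What the plan says.** The secondary endpoint in section 1.2.2 is "Recurrence free survival defined as the time between first treatment and disease recurrence". Recurrence is the only event named, and the word is not defined anywhere in the document.

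The analysis in section 11.2.2 is a single sentence: "Kaplan-Meier curves will be used to estimate the median recurrence free survival time". It gives no list of events, no censoring rule, and no rule for patients who progress before surgery or never have surgery.

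The tumor is in place at time zero. Section 5.1 requires that "The tumor is palpable and its size can be measured bidimensionally by tape, ruler or caliper technique", with a largest diameter above 2.0 cm. The synopsis gives the duration of administration as "Six months prior to definitive surgery".

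The population followed is everyone. Section 4.6.1, in the item on patients permanently taken off investigational product, says "All subjects will be followed for recurrence free survival". Section 6.8 adds "Patients who discontinue active treatment will be followed for recurrence free survival for up to 5 years".

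Progression on treatment is foreseen. Section 4.6.1 lists confirmed progression as a reason to stop durvalumab, and section 10.2 defines clinical progression, but only as a response category. Neither links it to recurrence free survival.

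**The concern.** Recurrence presupposes a disease-free state, and no patient is disease-free at first treatment. From first dose until surgery the clock runs, but the one event that the definition recognizes cannot occur in its ordinary sense. What can occur in that time is progression, and it has no place in the endpoint.

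The patients affected are those with the worst course: progression on treatment, in some cases so that definitive surgery is never done. The plan keeps them in follow-up for this endpoint and gives them no event. Two analysts could leave the same patient at risk and event-free, censor her, or count her, and each could claim to follow the protocol. In a population that may extend to T4c with any nodal status (section 5.1), and that section 11.3 expects to be mostly node positive and/or T3, such patients cannot be assumed absent.

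**Working it through.** **The plan's own figures.** None is given for recurrence free survival; it is neither sized nor tested. The only sized endpoint is mPEPI 0 (section 11.3), and its stated figures reproduce:

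- Probability of early termination at a 10% rate, with 0 or 1 success in 14: 0.9^14 + 14 × 0.1 × 0.9^13 = 0.585.
- Expected sample size: 14 + (1 − 0.5846) × 28 = 25.63.

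Neither uses recurrence free survival, so nothing in this point alters them.

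**Time before surgery.** There are six 28-day cycles (section 6.1.2), and end of treatment is 28 ± 7 days after C6D1 (section 8.2, footnote 16). C6D1 falls 5 × 28 = 140 days after C1D1, so end of treatment is at 140 + 28 = 168 days (161 to 175), which is 24 weeks or about 5.5 months. The wait from end of treatment to surgery is not stated and adds to this. Over five years of follow-up, 168/1826.25 = 9% of the time lies before end of treatment.

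**What each handling does to the late curve (illustration only).** Assumptions:

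- 42 patients, of whom k progress before surgery and never become disease-free. The documents do not give k; 0 to 5 is assumed.
- Surgery at day 168, that is 168/365.25 = 0.46 years.
- A constant recurrence rate after surgery, set from the historical 39.4% five-year recurrence in ER-positive disease quoted in section 2.1.1: −ln(1 − 0.394)/5 = 0.100 per year.

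For patients who reach surgery, the event-free proportion five years after first treatment is S = exp(−0.1002 × (5 − 0.46)) = 63.46%. The three handlings are then:

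- left at risk with no event: (k + (42 − k) × S)/42
- censored before surgery: S
- counted as an event: (42 − k) × S/42

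| k | left at risk | censored | counted | at risk minus counted | censored minus counted |
|---|---|---|---|---|---|
| 0 | 63.46% | 63.46% | 63.46% | 0 | 0 |
| 1 | 64.33% | 63.46% | 61.95% | 2.4 points | 1.5 points |
| 3 | 66.07% | 63.46% | 58.92% | 7.1 points | 4.5 points |
| 5 | 67.81% | 63.46% | 55.90% | 11.9 points | 7.6 points |

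Per patient, the first gap is 1/42 = 2.4 points whatever the recurrence rate. The second is S/42: 1.5 points here, and 0.874/42 = 2.1 points if the rate is 3% per year with surgery at 0.5 years.

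**The planned summary.** Under the same rate the median is ln 2/0.1002 = 6.9 years after surgery, or 7.4 years after first treatment. Follow-up ends five years after registration (section 8.2, footnote 17), so the median would probably not be reached and the curve itself would be what is read.

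**The case against.** First treatment is a legitimate, openly stated origin. It fits the follow-up clock, which runs from registration with treatment due within five working days (sections 8.2 and 12). This stands in full.

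Three stronger readings are tempting, and the documents do not support them.

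- A reader might infer that the result is overstated by a few points because the clock starts before surgery. Survival five years from first dose and five years from surgery are correct values of two different quantities. The plan names no five-year landmark, and follow-up would give only about 4.5 years after surgery.
- A reader might infer that anyone who progresses before surgery can never be an event. A patient who progresses, still has surgery and later relapses is an event at the later date. Because recurrence is undefined, a site might also record a new lesion as one. A strictly flat first half-year likewise depends on the narrowest reading of that word.
- A reader might infer that every such patient hides 2.4 points. That is the upper limit, reached only if she stays at risk without censoring. Section 11.2.2 has no censoring rule; if she is censored, the bad outcome is removed from the curve and does not improve it.

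It is also fair that the endpoint is untested and has no benchmark or threshold. That limits the weight of the point. It does not give these patients an event.

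**Conclusion.** The point holds in this form: the definition combines an origin at which every patient has disease with an event that requires her to have been free of it, and nothing elsewhere in the document makes progression before surgery an event. This is a fault in a stated definition, and it can give a misleading curve.

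The size depends on how many patients progress and never become disease-free, which the documents do not give. Relative to counting the event, each of 42 is worth up to 2.4 points on the late curve if left at risk, and about 1.5 points if censored under the constant rate and historical 39.4% used above. If there are none, this part of the effect is zero.

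The consequence is limited to a descriptive secondary endpoint. The mPEPI analysis, the two-stage rule and the sample size of 42 are unaffected. The point does not rest on how deaths are handled, which is a separate matter.

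**What to change.** In sections 1.2.2 and 11.2.2:

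- Keep first treatment as the origin and rename the endpoint event-free survival.
- Count as events disease progression before surgery, including progression that precludes definitive surgery, and recurrence after surgery. Define both terms.
- State how a patient who has no surgery for another reason is handled, and when patients are censored.
- Report the number who never reach definitive surgery.

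If recurrence free survival from surgery in patients rendered disease-free is also shown, make it supplementary. On its own it would still leave the worst outcomes off the curve.

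The cost is small. Tumor examination at each cycle, imaging at end of treatment and surgery are already scheduled (sections 8.2, 9.2 and 9.3), so no new procedure is needed. Section 13 limits data capture to endpoints and relevant patient information, so the team should confirm that the case report form holds the date of progression and either the date of surgery or the reason for none. The curve may look slightly worse. The change should be made before these data are analyzed.
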